1 ABBREVIATIONS USED IN THE PROTOCOL

Abbreviation	Term
AF	atrial fibrillation
AV	atrioventricular
BBB	bundle branch block
BVP	biventricular pacing
CRT	Cardiac Resynchronization therapy
ECG	electrocardiogram
EF	ejection fraction
EQ-5D	EuroQoL 5D
HBP	His bundle pacing
HF	heart failure
HFH	Heart Failure Hospitalization
HOT-CRT	HPCSP-optimized Trial of CRT
HPCSP	His-Purkinje conduction system pacing
ICD	implantable cardioverter defibrillator
KCCQ	Kansas City Cardiomyopathy Questionnaire
LBBB	left bundle branch block
LBBP	left bundle branch pacing
LV	left ventricular
LVEF	left ventricular ejection fraction
NYHA	New York Heart Association
RBBB	right bundle branch block
RV	right ventricular
sLVP	synchronized left ventricular pacing
VF	ventricular fibrillation
VT	ventricular tachycardia

2 ABSTRACT

Despite the great impact Cardiac Resynchronization therapy (CRT) utilizing biventricular pacing (BVP) has had on heart failure patients, one-third of patients do not respond to CRT, and CRT may result in worsening heart failure and increased mortality in some patients. We hypothesize that in patients with heart failure (HF) eligible for CRT as part of routine standard-of-care based on accepted Class I or Class II indications, His-Purkinje conduction system pacing (HPCSP)-optimized trial of CRT (HOT-CRT) may not only be safely achieved but will also be associated with superior echocardiographic and clinical outcomes compared to conventional BVP during CRT. We aim to determine the overall rate of successful HOT-CRT at the time of implant of CRT in a pilot study, collecting data in BVP and HOT-CRT on acute and mid-term outcomes at Geisinger. Primary outcomes include freedom from major complications and change in left ventricular ejection fraction (LVEF) at 6 months. To compare the effectiveness of HOT-CRT versus traditional CRT in patients with heart failure, patients will be randomized to either HOT-CRT or BVP and will remain blinded to their treatment allocation. Treating physicians will be aware of assignment in order to facilitate routine device follow-up. Echocardiographic evaluation will also be performed in a blinded manner. Crossover is permitted between treatment group allocation as follows: (1) If CS lead (BVP) cannot be placed due to difficult cannulation of the CS, limited branches at the posterolateral or lateral wall, or phrenic nerve capture, patients may then crossover to HOT-CRT. All efforts will be made to achieve CRT using CS lead. (2) HOT-CRT patients may crossover if HPCSP lead cannot be positioned with adequate stability and reasonable pacing output and acceptable electrical resynchronization cannot be achieved. Echocardiographic response to CRT (improvement in left ventricular ejection fraction) and a combination of clinical, electrocardiographic, and echocardiographic endpoints will be prospectively studied. Any complications will also be assessed prospectively, both acutely and throughout the study period.

3 BACKGROUND AND SIGNIFICANCE

Heart failure (HF) is one of the leading causes of hospitalization, morbidity and mortality in the United States. In addition, healthcare costs of heart failure in the United States exceed \$35 billion annually.¹ CRT utilizing BVP has made major improvements to symptoms and mortality in HF patients with New York Heart Association (NYHA) symptoms class II, III or ambulatory IV, left ventricular (LV) ejection fraction (EF) < 35% and widened QRS by electrocardiogram (ECG).^{2,3,4} Despite the great impact of CRT in HF, one-third of patients do not respond to CRT.⁵ In some patients, CRT may result in worsening heart failure and increased mortality. The anatomic location of the LV lead, patient specific characteristics, myocardial substrate and ECG

characteristics may affect clinical response. Novel approaches to improve CRT outcomes are necessary and several new approaches are evolving. Small studies have examined patients with intact intrinsic atrioventricular (AV) conduction and normal or near-normal conduction via the right bundle branch. In these patients, LV pacing synchronized to produce fusion with the intrinsic activation via the right bundle branch (sLVP) results in superior LV and right ventricular (RV) electrical activation and function compared to biventricular pacing. In a study using sLVP, patients with >50% sLVP had significantly decreased heart failure hospitalization and mortality compared to patients with <50% sLVP.⁶ However, this algorithm is limited by the need for patient's intact AV nodal conduction to allow for conduction to occur normally via the right bundle branch. Significant number of patients with heart failure require atrial pacing and or have long PR intervals limiting the utility of this approach. Recent studies suggest improved outcomes with His bundle pacing (HBP).⁷ HBP can correct underlying bundle branch blocks and thereby decrease or normalize QRS duration. Studies have shown high rates of hyper-response to CRT utilizing His bundle pacing.⁸ A randomized crossover study showed comparable benefits with HBP compared to standard CRT.⁹ A recent small pilot study (HisSync) comparing HBP with BVP could not demonstrate superiority with HBP due to high crossover rates.¹⁰ Nonetheless this study showed a trend towards improved clinical and echocardiographic outcomes with HBP compared to BVP. Many patients in these studies show partial correction of left bundle branch block (LBBB) with HBP. HBP can also provide robust AV synchronization in patients with long AV delays or AV nodal block. By maintaining normal conduction through the right bundle and part or most of the left bundle, HBP can provide clinical and hemodynamic benefits. Our early experience shows that His bundle Optimized LV pacing can combine AV synchrony with fusion LV pacing.¹¹ The QRS duration and morphology can mimic normal physiologic pattern in this situation. Permanent His bundle pacing utilizes FDA-approved clinical tools to precisely position the pacing lead at the His bundle region and stimulates the ventricles through the intrinsic His-Purkinje system, which results in synchronous electrical and mechanical activation. There is great clinical uncertainty for CRT utilization in HF patients "in the middle" with intermediate ECG criteria; QRS duration 130-149ms or non-LBBB morphology; currently Class IIa-IIb indications. This is a significant clinical problem because these patients with intermediate ECG criteria represented 40-45% of those enrolled in the large randomized trials that showed benefit of CRT. Even in these patients with right bundle branch block (RBBB), HBP has been shown to normalize conduction by recruiting the right bundle conduction.¹² Because of the ability of His-Purkinje conduction system pacing to achieve significant electrical resynchronization in the majority of patients undergoing CRT, this form of pacing has the theoretical potential to improve

clinical outcomes compared to BVP. Lack of direct comparison by means of randomized studies are the current limitations of this approach.

3.1 Hypothesis

We hypothesize that:

1. in patients with advanced heart failure and evidence of intraventricular conduction disease who meet criteria for CRT, HOT-CRT may be safely achieved and,
2. HOT-CRT will be associated with superior echocardiographic and clinical outcomes compared to conventional biventricular pacing (BVP) during CRT.

3.2 Specific Aim 1

To determine the overall rate of successful HOT-CRT at the time of implant of CRT. Patients randomized to HOT-CRT but who cannot be successfully implanted with a HPCSP lead will crossover to traditional coronary sinus (CS) lead position.

3.3 Specific Aim 2

To perform a pilot study to collect data in BVP and HOT-CRT on acute and mid-term outcomes at Geisinger. Acute outcomes include change in QRS duration pre-and post-pacing (degree of QRS narrowing) and incidence of major periprocedural complications (pericardial tamponade, need for lead revision, etc.). Mid-term outcomes include echocardiographic response at 6 months along with a composite clinical outcome of heart failure hospitalization, ventricular arrhythmias, crossover, and all-cause mortality.

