5.2.2 Inclusion Criteria

Eligible patients will be similar to those previously enrolled in the large randomized controlled trials and current Society guidelines^{18, 19} which support current indications for CRT. The following are the inclusion criteria for the HOT-CRT study:

1. Patients at least 18 years of age
2. Diagnosis is NYHA Class II, III, and ambulatory Class IV heart failure with either ischemic or nonischemic cardiomyopathy and patients with NYHA Class I symptoms and ischemic cardiomyopathy, with at least one of the following:
 - i. LV systolic dysfunction with LVEF \leq 35% and Evidence of bundle branch block with QRS duration $>$ 120 msec
 - ii. LV systolic dysfunction with LVEF \leq 50% and with need for $>$ 40% RV pacing

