5.5 Procedures & Study Timeline

Patients enrolled in the study will receive a permanent CIED (CRT-pacemaker or CRT-defibrillator) as clinically indicated. Patients will be centrally randomized by the study team with input from the biostatistician.

Procedure:

Patients randomized to biventricular pacing will undergo left ventricular lead placement in the coronary sinus venous branches.

Patients randomized to HOT-CRT will undergo CRT as described below. His bundle pacing lead will be placed initially to achieve CRT. If complete resynchronization is achieved (BBB normalization) but capture thresholds are high (1.5-2V), the lead may be placed in the distal conduction system (left bundle branch area). If only partial QRS narrowing is achieved, a coronary sinus lead may be placed and LV timing may be optimized to achieve maximal resynchronization. This will be at the discretion of the implanting physician.

Visit One - Pre-Implant

Enrolled subjects will undergo the following standard care procedures, unless noted as being completed for research purposes:

1. Clinical physical evaluation
2. Serum or urine pregnancy screen for women of child-bearing potential
3. Serum BNP or pro-BNP, baseline metabolic panel
4. Electrocardiogram
5. Transthoracic Echocardiogram (TEE) will be completed if it has not been done within the previous 3 months prior to Visit One.
6. Kansas City Cardiomyopathy Questionnaire (KCCQ) will be completed by the subject as part of the study
7. EuroQoL 5D (EQ-5D) will be completed by the subject as part of the study
8. Six Minute Walk Test (6MWT) will be administered by study staff to record distance as part of the study
9. NYHA functional class
10. Randomization – Subjects will be randomized by study staff in the study REDCap database to either HOT-CRT or standard BVP lead placement using a permuted block design. Patients will be blinded to randomization arm. Blocks of size 2 and 4 will be

randomly generated. Randomization will be stratified by LBBB and non-LBBB (right bundle branch block, RV pacing or narrow QRS) and by clinical site.

11. Collection of adverse events from time of consent until end of study participation

Visit Two – Day of Implant

1. Implant completed according to the assigned randomization arm by investigator
2. Electrocardiogram completed pre/post procedure
3. Device interrogation completed prior to hospital discharge
4. Adverse event collection

Visit Three – 2-week follow-up

1. Device Interrogation

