5.7 Secondary Endpoints

Secondary endpoints are as follows:

- Clinical: Composite of heart failure hospitalization, ventricular tachycardia (VT)/ventricular fibrillation (VF), crossover of treatment and any-cause mortality at 6 months will be assessed. NYHA functional class and quality of life will also be assessed.
- Electrocardiographic: Change in QRS duration between pre-implant and at hospital discharge, and 6 months will be performed. Arrhythmia occurrence (i.e., atrial fibrillation

(AF), nonsustained VT, VT or VF requiring device therapy) will be documented throughout the study period.

- Echocardiographic: Change in left ventricular end-systolic volume index, chamber dimension, and tissue-strain pre-implant, and at 6 months will be performed by readers blinded to treatment allocation.

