5.8.2 Statistical Power and Sample Size Considerations

Analysis will follow the “intent-to-treat” principle. That is, subjects will be analyzed based on their randomization allocation. A small number of patients might cross-over into the other arm so we will complete a secondary analysis using the per-protocol principle where subjects are analyzed based on their final treatment allocation. Data will be fully described using mean and standard deviation or median and inter-quartile range for continuous measures, and frequency and percentage for categorical variables. Baseline variables will be summarized by randomization arm to assess for balance. Any imbalance will be adjusted for in the estimation of the parameters of interest. Successful placement (Aim 1) will be summarized in the HOT-CRT group among those randomized to this group. The percentage and 95% confidence interval will be estimated. A logistic regression model will be fit to identify baseline factors that associate with success. The primary endpoint in Aim 2, change in LVEF, will be estimated along with the

standard deviation and 95% confidence interval. The difference in change between the randomization arms will also be estimated. No formal statistical inferences will be conducted in this study. Deliverables

Pilot study deliverables will be to establish feasibility, collect preliminary data, and further develop and refine infrastructure to test hypothesis(es) in a fully powered trial. We anticipate being able to identify specific clinical and health care utilizations endpoints during the pilot trial, which will be important to further investigate in a larger, powered trial. We hope to publish our findings and add to the generalizable knowledge to inform physicians, policy-makers, and the healthcare community of real-world outcomes.

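### QRS change is defined for all patients whatever their baseline QRS and without baseline-QRS adjustment: the arm comparison stays valid but loses precision, and the within-arm narrowing figures depend on case mix

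*Combined protocol and SAP*

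**What the plan says.** Section 3.3 (Specific Aim 2) names two acute outcomes, QRS change and major periprocedural complications. On the first it states: "Acute outcomes include change in QRS duration pre-and post-pacing (degree of QRS narrowing". The electrocardiographic endpoint in section 5.7, also given in section 5.1, is worded neutrally: "Change in QRS duration between pre-implant and at hospital discharge, and 6 months will be performed". Neither place names an analysis population, a subgroup or a covariate.

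Section 5.2.2 admits patients by at least one of two routes. The first needs LVEF of 35% or less and "Evidence of bundle branch block with QRS duration $>$ 120 msec". The second needs LVEF of 50% or less "and with need for $>$ 40% RV pacing", with no QRS requirement. Section 5.5 then says: "Randomization will be stratified by LBBB and non-LBBB (right bundle branch block, RV pacing or narrow QRS) and by clinical site". Narrow QRS is therefore expected, and it shares a stratum with two other baseline types. The hypothesis in section 3.1 is framed more tightly: "in patients with advanced heart failure and evidence of intraventricular conduction disease who meet criteria for CRT".

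Section 5.8.2 is descriptive and by intention to treat. Its only provision on baseline variables is "Any imbalance will be adjusted for in the estimation of the parameters of interest". Section 5.8.1 says that the pilot exists to estimate parameters for designing a larger study.

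**The concern.** The same change score means different things for different baseline QRS types. In a patient with bundle branch block it measures correction of a conduction delay, which is how sections 3 and 5.5 describe resynchronization. In a patient who is already RV-paced, the starting QRS is itself a paced one, so a reduction reflects replacing that pacing. In a patient with a narrow native QRS there is no delay to correct, and the word narrowing does not describe the aim.

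If these patients are summarized together, the within-arm mean depends on who happened to enrol, and the differences between types inflate the SD. Those two numbers are what a later trial would carry forward for this endpoint. An unadjusted comparison of arms also carries avoidable noise.

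**Working it through.** **The plan's own figure.** The only design figure concerns LVEF: SD 7.93 and 50 per arm (section 5.8.1). A single-arm t interval gives 2.0096 × 7.93 / √50 = 2.254, which reproduces the stated 2.25. No SD, effect or precision is stated for QRS change, so no figure in the plan changes.

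**How many patients could be concerned.** Section 5.8.1 assumes equal numbers above and below LVEF 35%. A patient above 35% cannot qualify by the first route. On the plan's own assumption, about half of the patients would therefore enter only by the route without a QRS criterion. Some of them may have bundle branch block or be RV-paced, and the narrow share is not given. I take 10% to 30%.

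**Illustration (all ms values are assumptions).** Wide-QRS patients change by −35 ms (HOT-CRT) and −20 ms (BVP). Narrow-QRS patients change by +10 and +35 ms. The SD within each type is 18 ms. The wide-to-narrow gap is 45 ms in one arm and 55 ms in the other, 50 ms on average. With narrow share p and 50 per arm:

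- mean = (1 − p) × wide + p × narrow
- SD = √(18² + p(1 − p) × 50²)
- SE of the difference = SD × √(2/50) = SD × 0.2

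| Narrow share | HOT-CRT mean | BVP mean | Difference | SD | SE of difference |
|---|---|---|---|---|---|
| 0% | −35 | −20 | −15 | 18.0 | 3.6 |
| 10% | −30.5 | −14.5 | −16 | 23.4 | 4.7 |
| 20% | −26 | −9 | −17 | 26.9 | 5.4 |
| 30% | −21.5 | −3.5 | −18 | 29.1 | 5.8 |

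At 20% the variance is 324 + 0.16 × 2500 = 724 against 324, a ratio of 2.2. A later trial sized on the unadjusted SD would need about 2.2 times the patients for this endpoint, for the same difference.

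**Other assumed values.** Take −40 and −20 ms for wide QRS, +5 and +30 ms for narrow QRS, and SD 20 ms. At 20% narrow the arm means are −31 and −10 ms and the difference is −21 ms (it is −20 ms with no narrow-QRS patients). The 95% half-width of the difference is 10.8 ms unadjusted and about 7.8 ms when the type is accounted for.

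**Effect of the existing stratification.** Chance imbalance in narrow QRS is not a further harm. With simple randomization, its SD at 20% is √(2 × 0.2 × 0.8 / 50) = 0.08, or 0.08 × 50 = 4 ms, and √(3.6² + 4²) = 5.4 ms, which is the SE already shown. Stratification by LBBB makes it smaller. For example, if 40% are non-LBBB and half of those are narrow, the imbalance SD is 0.4 × √(2 × 0.5 × 0.5 / 20) = 0.063, or 3.2 ms. The true sampling error is then √(3.6² + 3.2²) = 4.8 ms, although an analysis that ignores the strata would still report about 5.4.

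**The case against.** A reader might infer that the endpoint averages opposite effects and so does not measure resynchronization. The documents do not support that. Randomization makes expected baseline QRS equal in the two arms, so the difference in change estimates the difference in paced QRS. In the illustration both types favour HOT-CRT (−15 ms in wide QRS, −25 ms in narrow QRS). Only the within-arm changes differ in sign, and the pooled contrast keeps its direction and roughly its size.

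A reader might also suppose that a narrow QRS can only stay the same or widen with pacing. The documents do not say so, and it would not cover RV-paced patients who enter by the second route.

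Further points on the plan's side are fair. Pooling is inferred from silence; nothing forbids reporting by stratum. The term narrowing appears only in the aims, not in the endpoint definition. QRS change is one of two acute outcomes. Section 5.8.2 provides for adjustment when imbalance is seen, and the pilot makes no formal inferences. If few narrow-QRS patients enrol, the effect is negligible.

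These points limit the weight of the concern but do not remove it. Adjustment for observed imbalance names no variable or rule. It also cannot repair a within-arm mean and SD that vary with the mix of patients even when the arms are perfectly balanced.

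**Conclusion.** The point holds in a limited form. Eligibility and stratification both allow narrow and RV-paced baselines, while the QRS endpoint ignores baseline type. The between-arm estimate is valid but needlessly imprecise, and the within-arm narrowing and its SD should not be used to plan the larger trial without knowing the baseline mix. Over an assumed narrow share of 10% to 30%, the SE of the difference is 4.7 to 5.8 ms, against 3.6 ms without the mixture. The actual size is unknown, because it rests on a narrow-QRS share and ms values that the documents do not give. It is a minor matter, confined to an acute and secondary endpoint.

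**What to change.** In sections 5.7 and 5.8.2:

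- Estimate the between-arm difference in paced QRS duration at discharge and at 6 months. Adjust for baseline QRS duration, baseline QRS category (LBBB, RBBB or other wide, RV-paced, narrow) and the randomization strata. The four categories already contain the LBBB split, so site is the only further stratum term. With baseline QRS duration in the model, taking change as the outcome gives the same treatment estimate.
- Report within-arm QRS change separately by those categories. Keep the term narrowing for patients with bundle branch block, show RV-paced patients on their own rather than merged with them, and give paced QRS duration for narrow-QRS patients.
- Reconcile the population named in section 3.1 with the second entry route and the narrow-QRS component of the stratum.

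The cost is a few sentences and a few model terms; all the ECGs are already scheduled. The drawback is that some categories will be small, so their summaries will be imprecise.

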4 PRELIMINARY DATA

In patients with bundle branch blocks (BBB), capture thresholds to correct the BBB may limit the ability to achieve successful HBP. High pacing thresholds may lead to premature battery depletion. Recently an alternative form of conduction system pacing has gained significant momentum. By pacing distal to the site of conduction block in the proximal left bundle via deep lead placement in the interventricular septum, very low and stable capture thresholds can be achieved.^{13,14,15,16,17} This new approach, called left bundle branch pacing (LBBP), has been shown to achieve significant narrowing of the paced QRS and improve clinical outcomes in patients with LV dysfunction and LBBB. In short- and medium-term follow-up, this approach has been shown to be feasible in a very high percentage of patients.

5 STUDY DESIGN

5.1 Description

This is a randomized, prospective, single-blinded trial. Patients will be randomized to HOT-CRT versus BVP and will remain blinded to their treatment allocation. Both treatment options use standard-of-care, FDA-approved devices. The distinction is only in the allocation toward HOT-CRT and BVP. Treating physicians will be aware of assignment in order to facilitate routine device follow-up. Echocardiographic evaluation will also be performed in a blinded manner. Study physicians with the role of completing this evaluation will be blinded to lead placement.

Crossover is permitted between treatment group allocation if:

- CS lead (BVP) cannot be placed due to difficult cannulation of the CS, limited branches at the posterolateral or lateral wall, or phrenic nerve capture. These patients may then crossover to HOT-CRT. All efforts will be made to achieve CRT using CS lead.
- HOT-CRT patients may crossover if HPCSP lead cannot be positioned with adequate stability and reasonable pacing output and acceptable electrical resynchronization cannot be achieved.

Implant procedure will be per routine percutaneous access, as is standard for pacemaker and implantable cardioverter defibrillators (ICDs). All patients will receive FDA-approved cardiac resynchronization therapy pacemaker or defibrillator device, as per standard of care outlined for the patient.

Follow-up will be performed at 2 weeks post-implant for incision check and device interrogation, as is standard of care. In addition, routine device and clinical follow-up will be scheduled at 3, and 6 months, with remote device monitoring between scheduled visits, as needed.

Electrocardiography (i.e., ECG) will be performed pre-implant, prior to hospital discharge, and at 3- and 6-months post-discharge, as is standard of care. Echocardiography will be performed pre-implant, at 6 months to evaluate for change in left ventricular ejection fraction (LVEF), chamber dimension, and wall motion with strain imaging as is standard of care in the treatment of patients with advanced heart failure. NYHA functional class and quality of life, as measured

by the Kansas City Cardiomyopathy Questionnaire (KCCQ) and the EuroQoL 5D (EQ-5D), will be assessed pre-implant and at 6 months.

The primary clinical endpoint for the study (Aim 2) is change in left ventricular ejection fraction at 6 months. The primary safety endpoint (Aim 1) – freedom from major complications such as pericardial tamponade or need for CRT lead revision.

Secondary endpoints are as follows:

- Clinical: Composite of heart failure hospitalization, ventricular tachycardia (VT)/ventricular fibrillation (VF), crossover of treatment and any-cause mortality at 6 months will be assessed. NYHA functional class and quality of life will also be assessed.
- Electrocardiographic: Change in QRS duration between pre-implant and at hospital discharge, and 6 months will be performed. Arrhythmia occurrence (i.e., atrial fibrillation (AF), nonsustained VT, VT or VF requiring device therapy) will be documented throughout the study period.
- Echocardiographic: Change in left ventricular end-systolic volume index, chamber dimension, and tissue-strain pre-implant, and at 6 months will be performed by readers blinded to treatment allocation.

Regarding primary complication endpoints, complications will be assessed prospectively both acutely and throughout the study period, including:

- Procedure-related: pneumothorax, perforation, pericardial effusion, or hemorrhage
- System-related: implant site hematoma, implant site infection
- Lead-related: lead dislodgement, lead fracture, inability to pace due to high threshold, phrenic capture

Patients will be allocated to HOT-CRT or standard BVP (CS lead) prior to implant procedure. Randomization will be performed by the assigned biostatistician and use a randomly permuted block design. Blocks of size 2 and 4 will be randomly generated. Randomization will be stratified by LBBB and non-LBBB and clinical site.

Chart review will be performed for each enrolled patient upon study completion. The following events/data points will be collected to perform a survival analysis curve between the two randomized groups:

- Date of death and cause of death

- Heart failure hospitalization (HFH), date of HFH, and number of HFHs
- Atrial and ventricular arrhythmias as per device log
- Complications (i.e., lead revision, infection, device replacement, etc.)
- Last encounter date
- Last withdrawal date

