5.2.1 Approximate Number of Subjects

Approximately 100 Geisinger subjects will participate in this study; approximately 50 in the intervention arm, and approximately 50 in the control arm.

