5.3 Recruitment

Subjects selected for the study will be recruited from Geisinger Wyoming Valley, Geisinger Medical Center, and Geisinger Community Medical Center for participation in the study. Investigators will identify eligible subjects during one of their initial, standard care visits, describe the study procedures and invite them to participate in the study. The Informed Consent Form (ICF) will be provided to the subject and they will have ample time and opportunity to review and consider participation. Prior to performing any study procedures, the subject will sign the ICF and be considered enrolled at that point. Documentation of the consent process will be entered into the subject's Electronic Health Record (EHR). The subject will be assigned a Study ID Number upon enrollment and their data will be entered into the study's database.

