5.4.2 Approximate Duration of Study

This study will be completed in approximately 24 months. This includes 3 months of study start-up, a subject recruitment period of approximately 12 months, 6 months of subject follow-up from the time of last subject enrolled and 3 months for data analysis.

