5.8.1 Statistical Analysis Plan

This is a pilot study to collect data and estimate parameters that are needed to design a larger study. Therefore, the sample size is based on estimating the precision of the change in left ventricular ejection fraction (LVEF). If we assume an equal distribution of subjects with LVEF at baseline above or below 35%, then from the BLOCK-HF trial²⁰ we further assume that the standard deviation of change in LVEF at 6 months will be 7.93. With a sample size of 50 patients in each arm, we can estimate the precision of a 95% confidence interval (i.e., half-width) to be 2.25. A sample size of 50 was chosen due to budget limits.

Survival analysis will be conducted between the two randomized groups to assess time-to-event as an endpoint.

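### Randomization is stratified by LBBB status and site, but adjustment for these factors depends on imbalance being seen; always adjusting the LVEF difference for them is a small, almost free gain

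*Combined protocol and SAP*

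**What the plan says.** Sections 5.1 and 5.5 describe permuted-block randomization stratified by LBBB versus non-LBBB and by clinical site. Both give the block sizes: "Blocks of size 2 and 4 will be randomly generated". Section 5.5 adds: "Patients will be centrally randomized by the study team with input from the biostatistician". Section 5.3 names three recruiting sites, so there are 2 x 3 = 6 strata. Section 5.2.1 sets the size: "Approximately 100 Geisinger subjects will participate in this study", about 50 in each arm.

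Section 5.8.1 sizes the pilot on precision. It assumes that the "standard deviation of change in LVEF at 6 months will be 7.93" and gives a 95% half-width of 2.25 with 50 patients in an arm.

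Section 5.8.2 says that baseline variables will be summarized by arm to check balance and that estimates will be adjusted for whatever imbalance is found. It gives no criterion for imbalance and does not list LBBB status or site as covariates. It plans to estimate LVEF change with a standard deviation and a 95% confidence interval, and also to estimate the difference in change between arms. It rules out formal inference.

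**The concern.** The analysis does not carry through the structure of the randomization. When allocation is balanced within strata, the part of the outcome variance that lies between strata largely cancels from the difference between arms. A standard error that ignores the strata still counts that part, so the interval is wider than it needs to be.

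The adjustment rule in 5.8.2 is unlikely to repair this. It is triggered by observed imbalance, and stratified blocking makes imbalance on these two factors small by construction. The rule is therefore least likely to operate for the factors that the design singled out as important. It also leaves the choice of model until after the baseline tables have been seen, with no stated threshold.

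What is at stake is the precision and reproducibility of the between-arm LVEF difference, which the pilot is meant to supply to a larger trial.

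**Working it through.** **Inputs.** SD of LVEF change 7.93 and 50 per arm (5.8.1); two LBBB levels (5.1, 5.5); three sites (5.3). All 100 patients are taken to have a 6-month value, because the plan gives no dropout figure. The share of within-arm variance explained by LBBB status and site, R², is not in the documents; 0% to 20% is assumed here.

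**1. The plan's own figure.** One arm: t(0.975; 49) x 7.93 / √50 = 2.254, which reproduces the stated 2.25. It is the half-width for the mean change in a single arm, not for the difference between arms.

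**2. Between arms, unadjusted.** t(0.975; 98) x 7.93 x √(2/50) = 3.147, about 3.15.

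**3. Between arms, adjusted.** The model has an intercept, arm, LBBB status (1 term) and site (2 terms). Residual degrees of freedom are 100 − 5 = 95. Half-width = t(0.975; 95) x 7.93 x √(0.04 x (1 − R²)).

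| R² (assumed) | Half-width |
|---|---|
| 0% | 3.15 |
| 5% | 3.07 |
| 10% | 2.99 |
| 20% | 2.82 |

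The three lost degrees of freedom have no visible cost at R² = 0. The half-widths are proportional to the SD, so another SD rescales them all equally.

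**4. How likely is the trigger to fire?** With a largest block of 4, the arms can differ by at most 2 patients within a stratum. At the extreme that is 3 x 2 = 6 patients across the three strata of one LBBB level, and 2 x 2 = 4 across the two strata of one site. Extremes are rare. In simulation with an equal mix of 2s and 4s and six strata of 16 or 17, the overall arm difference averaged about 1.6 patients, with a 95th percentile of 4.

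**5. The printed block sizes.** These figures assume that someone sees every assignment in a stratum of 17 and that the two sizes are equally likely. The documents state neither.

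- Blocks of 2 and 4: about 71% of allocations guessed correctly (chance is 50%), about 10% with certainty.
- Blocks of 4 and 6: about 68% and 6%.
- Sizes 2 and 4 unknown to the guesser (2, 4, 6 and 8 treated as equally likely): certain calls fall to 0%, but accuracy stays at about 71%. Guessing whichever arm is behind needs no knowledge of the sizes.
- Sizes unknown, with an illustrative bias per point of prognostic difference between the patients chosen. Steering only on calls of at least 80%: about 0.08 for 2/4 and 0.14 for 4/6. On calls of at least 75%: 0.328 and 0.300. On any lean: 0.416 and 0.354. The ranking of the two mixes depends on the cut-off.

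**The case against.** **Against the adjustment point.** Stratified blocks already keep these factors near balance, the unadjusted difference is not biased by leaving them out, and an interval that is somewhat too wide errs on the safe side. The gain rests on an R² that no document supports. The trial is a pilot without formal inference, and 5.8.2 promises an interval for LVEF change without saying outright that the difference will carry one. Read literally, adjusting for any imbalance might even catch a one-patient difference in LBBB status.

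Most of this stands, and it keeps the point small. It does not remove it. The difference is an intended output, and it is of little use for planning without an interval. With no threshold for imbalance, two analysts could fit different models to the same data. Adjustment costs nothing visible even if R² is zero.

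**A stronger reading that might be inferred.** A reader might conclude that the printed block sizes expose the trial to selection bias: "Treating physicians will be aware of assignment in order to facilitate routine device follow-up"; "Investigators will identify eligible subjects during one of their initial, standard care visits"; and the implant is also done by an investigator. The documents do not support that as a finding. Allocation is central, block sizes vary at random, and no passage shows that anyone tracks a sequence. With "a subject recruitment period of approximately 12 months", accrual is about 100 / 6 / 12 = 1.4 patients per stratum per month, so a choice between candidates would seldom arise. The 71% is an upper bound, and withholding the sizes does not lower it. Replacing 2/4 with 4/6 lowers it by about 3 points, and once sizes are withheld the bias comparison can favour either mix. Dropping size 2 is therefore a matter of preference.

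**Conclusion.** The point holds as a minor improvement to the analysis. The plan stratifies on two factors and does not commit to using them when it estimates the between-arm LVEF difference; its adjustment rule is data-dependent and poorly suited to these factors. The size is a half-width of 3.15 that becomes 3.07 to 2.82 for an assumed R² of 5% to 20%, and no change if the strata explain nothing. This rests on the plan's SD of 7.93, complete data on 50 per arm and three sites.

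Two further inferences should not be drawn. The unadjusted analysis is not invalid or biased for this reason; its interval is only wider than necessary. And adjusting for the strata would not correct selection of patients within strata, had any occurred; the reason for it is precision and agreement with the design.

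**What to change.** In 5.8.2, add a sentence to this effect: the between-arm difference in LVEF change, with its 95% confidence interval, will be estimated from a linear model with terms for randomized arm, LBBB status and clinical site (three sites), whether or not baseline imbalance is observed. Adjustment for other imbalances can stay as now written. The cost is one sentence and three degrees of freedom.

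Optional only: move the block sizes from 5.1 and 5.5 to a document held by the biostatistician, leaving a statement that sizes vary at random. This removes certain guesses only for someone who has not read the current text, and it leaves the upper-bound guess rate at about 71%. No change to the block sizes themselves is requested.
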